## 5.6 Adherence/Compliance

- 5.6.1** To be considered compliant with study medication, a participant must take at least 75% of scheduled doses. This determination will be done at the end of study by WF NCORP statisticians. Patients should be encouraged to remain on study and take the study medication even if they are known to be noncompliant with more than 25% of scheduled doses.
- 5.6.2** Compliance is monitored by daily diaries completed by the participant that are systematically collected weekly during radiation therapy and then monthly until 4 months post RT. In addition, compliance is monitored when appointments are made and when medication tolerance is assessed by the study team over the phone at week 14 and week 18. During the week 14 and 18 week phone contacts, participants should return study diaries via mail or in-person to the site study team. These data are entered into the study database for analyses by our biostatistician every 6 months when the study is reviewed by our DSMB.

## 6. PHARMACEUTICAL INFORMATION

### 6.1 Ramipril (IND-Exempt)

#### IND Status

The risks associated with Ramipril are not significantly increased in the proposed study population. The major risk of Ramipril in the non-hypertensive population is hypotension (11%). Ramipril has been used to treat several conditions in non-hypertensive patients including heart failure, post-myocardial infarction prophylaxis, and diabetic nephropathy and has been found to be safe in these settings. Furthermore, Ramipril is a generically available drug, and we are not conducting the proposed study in order to change the labelling instructions for Ramipril. A 10 mg dose of Ramipril was administered in 1,048 hypertensive and normotensive patients at risk of cardiovascular events and tolerability was generally considered to be good to excellent. The HOPE study was a randomized trial of 10 mg dose of Ramipril vs placebo for cardioprevention in over 9500 patients in which 50% of the study population was normotensive at the beginning of the study. A recent analysis of 160 patients treated with GBM at Wake Forest showed no difference in survival in patients treated with ACE inhibitors as compared to patients who were not treated with ACE inhibitors. As such, the risks associated with Ramipril are not significantly increased in the study population and therefore, an IND is not required.

### 6.2 Reported Adverse Events and Potential Risks

#### 6.2.1 Patients Taking Ramipril for Hypertension

Altace® (Ramipril) has been evaluated for safety in over 4,000 patients with hypertension; of these, 1,230 patients were studied in US controlled trials, and 1,107 were studied in foreign controlled trials. Almost 700 of these patients were treated for at least one year. The overall incidence of reported adverse events was similar in Altace® and placebo patients. The most frequent clinical side effects (possibly or probably related to study drug) reported by patients receiving Altace® in US placebo-controlled trials were: headache (5.4%), “dizziness” (2.2%) and fatigue or asthenia (2.0%), but only the last was more common in Altace® patients than in patients given placebo. Generally, the side effects were mild and transient, and there was no relation to total dosage within the range of 1.25 to 20 mg. Discontinuation of therapy because of a side effect was required in approximately 3% of US patients treated with Altace®. The most common reasons for discontinuation were cough (1.0%), “dizziness” (0.5%), and impotence (0.4%).

Of observed side effects considered possibly or probably related to study drug that occurred in US placebo-controlled trials in more than 1% of patients treated with ALTACE®, only asthenia (fatigue) was more common on ALTACE® than placebo (2% vs 1%).

	Altace® (n=651)		Placebo(n=286)	
	n	%	n	%
Asthenia (Fatigue)	13	2	2	1

In placebo-controlled trials, there was also an excess of upper respiratory infection and flu syndrome in the Ramipril group, not attributed at that time to Ramipril. As these studies were carried out before the relationship of cough to ACE inhibitors was recognized, some of these events might represent

Ramipril-induced cough. In a later 1-year study, increased cough was seen in almost 12% of Ramipril patients, with about 4% of these patients requiring discontinuation of treatment.

### 6.2.2 Patients Taking Ramipril for Heart Failure Post Myocardial Infarction

Adverse reactions (except laboratory abnormalities) considered possibly/probably related to study drug that occurred in more than one percent of patients and more frequently on Ramipril are shown below. The incidences represent the experiences from the AIRE study. The follow-up time was between 6 and 46 months for this study.

#### Percentage of Patients with Adverse Events Possibly/ Probably Related to Study Drug

Placebo-Controlled (AIRE) Mortality Study:

Adverse Event	RAMIPRIL (N=1004)	PLACEBO (N=982)
Hypotension	11	5
Cough Increased	8	4
Dizziness	4	3
Angina Pectoris	3	2
Nausea	2	1
Postural Hypotension	2	1
Syncope	2	1
Vomiting	2	0.5
Vertigo	2	0.7
Abnormal Kidney Function	1	0.5
Diarrhea	1	0.4

HOPE Study:

Safety data in the HOPE trial were collected as reasons for discontinuation or temporary interruption of treatment. The incidence of cough was similar to that seen in the AIRE trial. The rate of angioedema was the same as in previous clinical trials (see WARNINGS in the package insert).

	RAMIPRIL(N=4645)	PLACEBO(N=4652)
	%	%
Discontinuation at any time	34	32
Permanent discontinuation	29	28
Reasons for stopping Cough	7	2
Hypotension or Dizziness	1.9	1.5
Angioedema	0.3	0.1

Other adverse experiences reported in controlled clinical trials (in less than 1% of Ramipril patients), or rarer events seen in post-marketing experience, include the following (in some, a causal relationship to drug use is uncertain):

**Body As a Whole:** Anaphylactic reactions. (See WARNINGS in the package insert.)

**Cardiovascular:** Symptomatic hypotension (reported in 0.5% of patients in US trials) (See WARNINGS and PRECAUTIONS in the package insert), syncope and palpitations.

**Hematologic:** Pancytopenia, hemolytic anemia and thrombocytopenia.

**Renal:** Some hypertensive patients with no apparent pre-existing renal disease have developed minor, usually transient, increases in blood urea nitrogen and serum creatinine when taking ALTACE®, particularly when ALTACE® was given concomitantly with a diuretic. (See WARNINGS in package insert.) Acute renal failure.

**Angioneurotic Edema:** Angioneurotic edema has been reported in 0.3% of patients in US clinical trials. (See WARNINGS in package insert.)

**Gastrointestinal:** Hepatic failure, hepatitis, jaundice, pancreatitis, abdominal pain (sometimes with enzyme changes suggesting pancreatitis), anorexia, constipation, diarrhea, dry mouth, dyspepsia, dysphagia, gastroenteritis, increased salivation and taste disturbance.

**Dermatologic:** Apparent hypersensitivity reactions (manifested by urticaria, pruritus, or rash, with or without fever), photosensitivity, purpura, onycholysis, pemphigus, pemphigoid, erythema multiforme, toxic epidermal necrolysis, and Stevens-Johnson syndrome.

**Neurologic and Psychiatric:** Anxiety, amnesia, convulsions, depression, hearing loss, insomnia, nervousness, neuralgia, neuropathy, paresthesia, somnolence, tinnitus, tremor, vertigo, and vision disturbances.

**Miscellaneous:** As with other ACE inhibitors, a symptom complex has been reported which may include a positive ANA, an elevated erythrocyte sedimentation rate, arthralgia/arthritis, myalgia, fever, vasculitis, eosinophilia, photosensitivity, rash and other dermatologic manifestations. Additionally, as with other ACE inhibitors, eosinophilic pneumonitis has been reported.

**Fetal/Neonatal Morbidity and Mortality.** See WARNINGS in package insert:  
Fetal/Neonatal Morbidity and Mortality.

**Other:** Arthralgia, arthritis, dyspnea, edema, epistaxis, impotence, increased sweating, malaise, myalgia, and weight gain.

**Post-Marketing Experience:** In addition to adverse events reported from clinical trials, there have been rare reports of hypoglycemia reported during ALTACE® therapy when given to patients concomitantly taking oral hypoglycemic agents or insulin. The causal relationship is unknown.

### Clinical Laboratory Test Findings

**Creatinine and Blood Urea Nitrogen:** Increases in creatinine levels occurred in 1.2% of patients receiving ALTACE® alone, and in 1.5% of patients receiving ALTACE® and a diuretic. Increases in blood urea nitrogen levels occurred in 0.5% of patients receiving ALTACE® alone and in 3% of patients receiving ALTACE® with a diuretic. None of these increases required discontinuation of treatment. Increases in these laboratory values are more likely to occur in patients with renal insufficiency or those pretreated with a diuretic and, based on experience with other ACE inhibitors, would be expected to be especially likely in patients with renal artery stenosis. (See WARNINGS and PRECAUTIONS in package insert.) Since Ramipril decreases aldosterone secretion, elevation of serum potassium can occur. Potassium supplements and potassium-sparing diuretics should be given with caution, and the patient's serum potassium should be monitored frequently. (See WARNINGS and PRECAUTIONS in package insert.)

**Hemoglobin and Hematocrit:** Decreases in hemoglobin or hematocrit (a low value and a decrease of 5 g/dL or 5% respectively) were rare, occurring in 0.4% of patients receiving ALTACE® alone and in 1.5% of patients receiving ALTACE® plus a diuretic. No US patients discontinued treatment because of decreases in hemoglobin or hematocrit.

**Other (causal relationships unknown):** Clinically important changes in standard laboratory tests were rarely associated with ALTACE® administration. Elevations of liver enzymes, serum bilirubin, uric acid, and blood glucose have been reported, as have cases of hyponatremia and scattered

incidents of leukopenia, eosinophilia, and proteinuria. In US trials, less than 0.2% of patients discontinued treatment for laboratory abnormalities; all of these were cases of proteinuria or abnormal liver-function tests.

### **6.3 Availability**

Ramipril is available for oral administration in 1.25, 2.5, 5, and 10 mg capsules. The drug will be obtained, packaged, and distributed by McKesson Corporation (Winston-Salem, NC). McKesson Corp. will also provide storage and inventory for the study drug. Ramipril will be provided to study participants in 1.25 mg capsules at no cost. The Wake Forest NCORP Research Base will be providing all funding for Ramipril.

### **6.4 Agent Distribution**

Ramipril will be distributed by McKesson, Corp. Winston-Salem, NC ([name]; [contact]). McKesson, Corp. will distribute Ramipril directly to participating sites following enrollment of study patients. Ramipril will be provided to participants at no cost.

### **6.5 Agent Accountability**

The Site Investigator, or a responsible party designated by the Site Investigator, must maintain a careful record of the inventory and disposition of all agents received from McKesson using the NCI Drug Accountability Record Form (DARF) which can be found using the following link [https://ctep.cancer.gov/forms/docs/agent\\_accountability.pdf](https://ctep.cancer.gov/forms/docs/agent_accountability.pdf). The Site Investigator is required to maintain adequate records of receipt, dispensing and final disposition of study agent. On dispensing record, note quantities and dates study agent was dispensed to and returned by each participant.

### **6.6 Packaging and Labeling**

When a patient is enrolled to the study, local NCORP site should complete a Drug Order Request Form located in REDCap and fax to McKesson Corporation. Upon receipt of the request form, McKesson Corp. will confirm your site is approved for the study and will ship the drug to the local NCORP site. McKesson Corp. will call the local NCORP site Study Contact person to confirm the order was received. They will require the following information from the site:

- Patient Full Name or Initials
- Site Shipping Address and phone number
- Doctor's name

For all drug shipments from McKesson Corp., a packing slip will be enclosed that includes the date and quantity of drug provided, patient name/initials, study ID number, drug identification including lot number and expiration date.

All drug orders are shipped Priority Overnight delivery in a box designed to maintain temperature stability.

Once study drug is received at the local NCORP site, the designated site coordinator validates that the contents of the package (study medication received) matches the information provided on the packing slip. The inventory and disposition of Ramipril pills must be recorded using the NCI Drug Accountability Record Form (DARF). See section 6.5 Agent Accountability.

The first shipment of Ramipril per patient will contain a single bottle of 133 capsules. This shipment will provide the patient with drug through the first 6 weeks of treatment (Week 1-6 of RT). Prior to the completion of the first 6 weeks of treatment, McKesson Corp. will confirm the patient needs additional study drug, before shipping it to the local NCORP site. This second patient-specific shipment will contain a maximum of four bottles of Ramipril, containing 112 (1.25 mg) capsules each. This second shipment will last the patient for the final 4 months of Ramipril treatment, through Week 22 (4 Month Post-RT).

## **6.7 Storage**

Ramipril should be stored at room temperature per package insert.

## **6.8 Agent Destruction/Disposal**

Participating sites will dispose of unused portions of Ramipril according to their institution's SOPs.

## 7. CLINICAL EVALUATIONS AND PROCEDURES

### 7.1 Schedule of Events(A)

Evaluation/ Procedure	Enrollment	Baseline (B)	Titration of drug during RT (Wk 1-3)	During RT (Wk 4-5)	RT Completion (Wk 6)	1-month post RT (Wk 10)	2- & 3-Month post RT (Wk 14, 18) Phone Call	4-month post RT (Wk 22)	5- month post RT Wk 26) Phone Call
Eligibility/Enrollment	X								
Patient Demographics	X								
Medical History (1)		X				X		X	
Concurrent Medications & Supplements		X	X	X	X	X	X	X	X
Physical Exam (1)		X				X		X	
Blood Pressure		X	X	X	X	X		X	
Comprehensive Metabolic Panel (D)		X	X	X	X	X			
ECOG Performance Status		X							
Serum or Urine βHCG (2)		X							
ApoE Genotype (C)		X							
MRI/CT Brain (3)		X				X		X	
Toxicity Assessment			X	X	X	X			
Adverse Event Reporting			X	X	X	X	X	X	X
Medication Diary		X	X	X	X	X	X	X	
Pill count (Unused Study Agent)					X	X		X	
Ramipril Administration			X	X	X	X	X		
TTFields or Optune® Device						X	X	X	
Chemoradiation Summary					X				
Off Agent (E)			-----Only if applicable -----						X
Off Study (F)			-----Only if applicable -----						X
Cognitive & PRO Testing									
HVLT-R		X			X	X		X	
Trail Making Test, Part A		X			X	X		X	
Trail Making Test, Part B		X			X	X		X	
COWAT		X			X	X		X	
EORTCLQ-30/BN20		X			X	X		X	
Shipley Institutional of Living Scale		X							

(A) Refer to Section 7.3 for details of each evaluation or procedure

(B) Baseline evaluations and labs are required within 14 days of enrollment, excluding MRI. (Section 4.1.7).

(C) Research test only; refer to Section 9.0 for details.

(D) Inclusive of creatinine, potassium, GFR, Total Bilirubin, AST and ALT. It should be noted that CMPs on Week 1, 2, 3, 4, 5, & 6 during RT should be drawn only after  $\geq 4$  doses of current Ramipril dose has been taken by the patient. CMPs should be analyzed through LabCorp and paid by the study directly to LabCorp. If sites chose to use CMPs from local institutional labs for toxicity assessments, LabCorp CMPs should still be drawn. Sites should keep the same lab for toxicity assessments for all Week 1-6 labs for each patient. At Baseline and 1 month post-RT standard of care local labs will be used for the study.

(E) All study assessments should still be completed, unless patient is unwilling or withdraws consent.

(F) If the patient is going Off Study, complete all forms for the current visit, as well.

(1) Can be obtained  $\leq 14$  days prior to enrollment

- (2) Negative serum or urine pregnancy test required within 14 days prior to enrollment for women of childbearing potential. Results may be used from routine local lab.
- (3) MRI/CT Brain scans at the indicated time points are considered standard of care per national guidelines. As per section 4.1.7, all available brain MRI or CT imaging reports from surgery to study completion must be submitted. This includes any post-operative or pre-radiation scan reports. Treating physician assessment of tumor response – i.e. response, progression or stable disease – will be captured for each completed imaging study.

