MRI/CT Brain: MRI Brain will be completed per standard of care at each study site. Sites are asked to provide MRI final reports with the specific visit form. As per section 4.1.7, patients who are unable to undergo MRI scanning should have CT brain scans done as per this schedule. Treating physician assessment of tumor response – i.e. response, progression or stable disease – will be captured for each completed imaging study.

Toxicity Assessments: Assessments by the study team will be done from Week 1 of RT and the start of Ramipril to 5-month post RT (end of study). This time period includes 30 days after treatment with Ramipril. Refer to section 6.2 for reported adverse events and risks when taking Ramipril.

Adverse Event Reporting: Refer to Section 10 of the protocol for specifics.

**Medication Diary:** Each patient is asked to fill in a Ramipril Medication diary and return it to the study team weekly during radiation therapy (weeks 1-6), and monthly on 1- and 4- month post RT visit. Since 2- and 3- month visits can be phone calls, the patient will need to mail back these diaries to the study team. Refer to Appendix D for a Ramipril Medication diary.

**Pill Count:** Patients will be asked to bring pill bottles to visit. Study team will count and record pills given, remaining and taken on the visit CRF.

**Ramipril Administration:** This study drug will be provided at no charge to patients for oral administration daily from Week 1 RT to post 4-month RT (Week 22). Study team will be required to order, distribute and inventory study drug. Refer to Sections 6.3 – 6.8 and for titration schedule 5.1.2 for details.

**Chemoradiation Summary:** At the RT Completion (Week 6) visit, a summary of the standard of care chemotherapy and radiation therapy will be gathered.

**Off Agent:** Use this form when a patient goes Off Agent either at the completion of study drug administration per protocol or at the time of early discontinuation. All study assessment should be continue to be completed, unless the patient is unwilling or withdraws consent. LabCorp samples do not need to be collected after the patient is Off Agent. Please use local labs to complete assessment information in REDCap.

**Off Study:** Use this form when a patient goes Off Study by either withdrawing consent or completing the study. This form serves as a way to track the patient status.

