## **10.1 Adverse Events (AEs)**

### **10.1.1 Reportable AEs**

Following the guidance in Section 10.3, any reportable AEs that occur after the informed consent is signed and baseline assessments are completed should be recorded on the REDCap AE CRF whether or not related to study agent, as detailed below.

**The prompt reporting of adverse events is the responsibility of each investigator engaged in clinical research, as required by Federal Regulations**

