**10.1.4 Assessment of Relationship of AE to Treatment**

The possibility that the AE is related to study agent will be classified as one of the following attribution: Unrelated, Unlikely, Possible, Probable, Definite.

**Attribution:** An assessment of the relationship between the adverse event and study agent/intervention, using the following categories.

ATTRIBUTION	DESCRIPTION
Unrelated	The AE is clearly NOT related to the study agent (or product)/intervention
Unlikely	The AE is doubtfully related to study agent /intervention
Possible	The AE may be related to study agent/intervention
Probable	The AE is likely related to study agent/intervention
Definite	The AE is clearly related to study agent/intervention

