## **12.7 Evaluation of Toxicity**

### **Evaluation of Toxicity and Adverse Effects of Ramipril**

All patients will be evaluable for toxicity from the time of their first treatment with Ramipril. Toxicities will be quantified using the CTCAE v5.0 for Toxicity and Adverse Event Reporting. Fisher exact tests will be used to assess treatment differences in the incidence of individual toxicities, and logistic regression will be used to assess treatment differences in the incidence of any grade 3 or higher toxicity possibly, probably or likely related to Ramipril adjusting for baseline patient characteristics. In order to rule out cytoprotection of tumor by Ramipril, response rates will be compared to historical controls from RTOG 0825.

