**Are there any expected adverse effects?**

If you experience any of the following mild effects and feel they are related to your study medication (Ramipril), write them in the “comments” area. Discuss these with your research coordinator. Blurred vision, confusion, dizziness, faintness or lightheadedness when getting up suddenly from a lying or sitting position, sweating, unusual tiredness or weakness, cough, headache. There may be some risks that the study doctors do not yet know about.

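### No toxicity grade is taken before the first Ramipril dose and 12.7 has no new-or-worsened rule, so its individual-toxicity incidences may include symptoms that were already present

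*Combined protocol and SAP*

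**What the plan says.** Section 7.1 lists "Toxicity Assessment" as a row of its own, separate from adverse event reporting. It is blank at Enrollment and Baseline and marked for Weeks 1-3, Weeks 4-5, Week 6 and Week 10. The text in 7.3 agrees on the start: "Assessments by the study team will be done from Week 1 of RT and the start of Ramipril".

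Section 12.7 sets the analysis window: "All patients will be evaluable for toxicity from the time of their first treatment with Ramipril". Grading is by CTCAE v5.0. Two toxicity analyses follow:

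- Individual toxicities: "Fisher exact tests will be used to assess treatment differences in the incidence of individual toxicities". No attribution condition is attached.
- A logistic model for "any grade 3 or higher toxicity possibly, probably or likely related to Ramipril adjusting for baseline patient characteristics". This one is limited by attribution.

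Adverse events are handled separately. Section 10.1.1 covers "any reportable AEs that occur after the informed consent is signed and baseline assessments are completed", and 10.1.4 assigns each a relationship on a five-level scale. Neither 12.7 nor any other section defines a treatment-emergent event or says how a condition present before dosing is to be counted.

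**The concern.** Toxicity is measured repeatedly but has no starting value, whereas blood pressure, the metabolic panel, the cognitive tests and the quality-of-life questionnaires all have a Baseline mark. When the first toxicity form is completed, Ramipril and radiotherapy have begun, and usually temozolomide too. A headache recorded at Week 1 cannot be told from one that was there at enrollment unless someone looks outside the toxicity data.

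This matters because the population is likely to be symptomatic and its symptoms overlap with the drug's listed effects. ECOG 0 to 2 is eligible, and Appendix A defines grade 1 as having symptoms. The acute-toxicity text in 5.1.1.2 names headaches, seizures and weakness as brain tumour symptoms. The patient diary in Appendix D lists as possible Ramipril effects "Blurred vision, confusion, dizziness, faintness or lightheadedness when getting up suddenly from a lying or sitting position", followed by tiredness or weakness and headache among others, and 6.2 includes convulsions among reported events.

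At stake is the accuracy of the per-toxicity rates, which go to the DSMB every six months (11.4, 12.6) and would describe the drug's tolerability in this population.

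**Working it through.** **The plan's own figures.** The documents state no toxicity rate for this trial, so there is none to reproduce. The only figure borrowed below is the denominator of 75 from 12.2, which does reproduce: for 65% against 80%, one-sided 0.05 and 90% power, n = [(1.645 × √(0.65 × 0.35) + 1.282 × √(0.80 × 0.20)) / 0.15]² = 74.78, rounded up to 75. The point does not depend on it.

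**Which data could carry the problem.**

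1. *The adverse event form.* The onset condition in 10.1.1 keeps an unchanged earlier symptom out. But 10.3 restricts this form to unexpected grade 3 events attributed to the intervention, unexpected grade 4 events, and all grade 5 events. Grade 1-2 events and expected grade 3-4 events are not collected there.
2. *The Toxicity Assessment.* An expected low-grade headache or dizziness can therefore be captured only here or on another visit form. The protocol states no onset condition for this assessment. Sections 11.4 and 12.6 also list toxicities and adverse events as separate items.
3. *The grade 3 or higher model.* It keeps only Ramipril-attributed events, so those judged Unrelated or Unlikely drop out. Some misattribution of overlapping symptoms could remain.
4. *The individual-toxicity tests.* They have no attribution condition, no baseline grade and no worsening rule. This is where the exposure lies.
5. *Retention.* It is defined by doses taken and completion of the cognitive battery (1.1.1, 8.1), so toxicity grades do not enter it.

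**Possible size.** Let b be the share of patients with a symptom before the first dose and t the new-event rate among the rest. If every earlier symptom is recorded again on study, then

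recorded rate = b + (1 − b) × t.

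Both b and t are assumptions. With t = 5% and 75 patients:

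| b | Calculation | Recorded rate | Patients of 75 |
|---|---|---|---|
| 0% | 0 + 1.00 × 0.05 | 5.0% | 3.8 |
| 5% | 0.05 + 0.95 × 0.05 | 9.8% | 7.3 |
| 10% | 0.10 + 0.90 × 0.05 | 14.5% | 10.9 |
| 20% | 0.20 + 0.80 × 0.05 | 24.0% | 18.0 |

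The excess over t is b × (1 − t): zero when b is zero and close to b when t is small. If only some earlier symptoms are re-recorded, the excess shrinks in proportion.

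**Direction in a comparison.** Section 12.7 speaks of treatment differences, but the trial has one arm, and RTOG 0825 is named there only for response rates. If an external comparator is used for toxicity, the effect on the difference depends on how that source counted pre-existing symptoms, which the documents do not say.

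**The case against.** The other side has a good deal to say, and most of it limits the point without removing it.

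- *Some pre-dose information exists.* Baseline includes history, physical examination, blood pressure, a metabolic panel and the QLQ-C30/BN20, which covers headache, seizures, drowsiness, fatigue and nausea. Creatinine, potassium, liver enzymes and blood pressure have numeric baselines, so renal, potassium and hypotension effects can be judged against a starting value. This stands. But the questionnaires are patient-rated scales, no dizziness, cough or faintness item is listed in 7.6.2, and 12.7 does not say that any of this will be used to remove earlier symptoms.
- *The forms are not shown.* Appendix B lists a baseline data collection form whose fields are not in the documents. It might grade symptoms, so a reader should not infer that a pre-dose grade is certainly never recorded or could never be reconstructed. The protocol simply does not call for one.
- *Surgery.* Criterion 4.1.4 requires recovery from surgery before enrollment, so the concern rests on tumour symptoms and not on surgical effects.
- *Importance.* Section 1 has no toxicity objective. The decision to proceed rests on retention, and 12.2 designs the next trial from the effect size and the dropout rate. This stands and keeps the point secondary.

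A reader might also take the drug-related headache or dizziness rates in 6.2.1 as t, add a high assumed b, and conclude that the rates would be inflated many times over. The documents do not support that. Those rates are drug-attributed figures from hypertension trials, where neither symptom was more common than on placebo, and adding them to an unattributed prevalence mixes different quantities. Any multiple obtained this way mainly reflects the chosen b.

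**Conclusion.** The point holds as a limited one. The plan schedules no toxicity grade before the first dose and gives no rule for counting only new or worsened events, so the unfiltered individual-toxicity incidences in 12.7 may include symptoms present before Ramipril. Any such bias in those incidences is upward. Its size is unknown because the documents give no pre-dose prevalence. The illustration, from no excess at b = 0 to 24% recorded against 5% new at b = 20%, assumes that every earlier symptom is recorded again.

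The stronger reading, that pre-existing symptoms will be counted as Ramipril toxicity throughout, does not follow. Reportable adverse events must begin after baseline, the grade 3 or higher model is limited by attribution and so is less affected, and retention is not affected. The conclusion also assumes that the individual toxicities in 12.7 draw on the Toxicity Assessment or similar visit forms. The protocol implies this by listing toxicities and adverse events separately, but does not state it.

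**What to change.** Make three linked edits:

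1. In 7.1, add a Baseline mark to the Toxicity Assessment row, using the same CTCAE v5.0 assessment, completed before the first dose.
2. In 7.3, start toxicity assessments at Baseline.
3. In 12.7, state that an individual toxicity counts only when its worst on-study grade exceeds the patient's baseline grade.

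If the baseline form already grades these symptoms, it is enough to say so in 7.1 and 7.3 and add the sentence to 12.7. The cost is a few minutes of site time per patient at a visit that already includes history and examination. The edits change what is collected and counted, and leave treatment rules and the primary analysis as they are.
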